13.0 PARTICIPANTS

13.1 IRB Review and Informed Consent

This protocol and the informed consent document (Appendix I) and any subsequent modifications will be reviewed and approved by the IRB or EC responsible for oversight of the study. A signed consent form will be obtained from the participant. The consent form will describe the purpose of the study, the procedures to be followed, and the risks and benefits of participation. A copy of the consent form will be given to the participant, and this fact will be documented in the participant's record.

13.2 Participant Confidentiality

All laboratory specimens, evaluation forms, reports, and other records that leave the site will be identified by coded number only to maintain participant confidentiality. All records will be kept locked. All computer entry and networking programs will be done with coded numbers only. Clinical information will not be released without written permission of the participant, except as necessary for monitoring by the ACTG, IRB/EC, NIAID, OHRP, **other local, US, and international regulatory entities** as part of their duties, or the industry supporter or designee.

13.3 Study Discontinuation

The study may be discontinued at any time by the ACTG, IRB/EC, NIAID, OHRP, or other country-specific government agencies as part of their duties to ensure that research participants are protected, or the industry supporter or designee.

14.0 PUBLICATION OF RESEARCH FINDINGS

Publication of the results of this trial will be governed by ACTG policies. Any presentation, abstract, or manuscript will be made available for review by the industry supporter prior to submission.

15.0 BIOHAZARD CONTAINMENT

As the transmission of HIV and other blood-borne pathogens can occur through contact with contaminated needles, blood, and blood products, appropriate blood and secretion precautions will be employed by all personnel in the drawing of blood and shipping and handling of all specimens for this study, as currently recommended by the Centers for Disease Control and Prevention and the National Institutes of Health.

All dangerous goods and materials, including diagnostic specimens and infectious substances, must be transported using packaging mandated by CFR 42 Part 72. Please refer to instructions detailed in the International Air Transport Association (IATA) Dangerous Goods Regulations.

1.1 Purpose

This Primary Statistical Analysis Plan (SAP) describes the primary and secondary outcome measures and additional outcome measures of the ACTG A5354 study that will be included in the primary manuscript, and which address, at a minimum, the major primary and secondary objectives of the study. The Primary SAP outlines the general statistical approaches that will be used in the analysis of the study. It has been developed to facilitate discussion of the statistical analysis components among the study team, and to provide agreement between the study team and statisticians regarding the statistical analyses to be performed and presented in the primary analysis report. It also describes the results for the primary and secondary outcome measures that will be posted on ClinicalTrials.gov.

A subset of these analyses (as described herein) will form the basis of reports provided to the Study Monitoring Committee (SMC) while the study is ongoing. This analysis plan therefore includes the key analyses that might lead to modification or termination of the study, and hence form the core of any presentation or publication used to disseminate the primary conclusions of the study. However, it is recognized that this analysis plan may be modified by the study team as new information becomes available outside of the study, or to reflect recommendations made by the SMC or changes in the study design. In addition, some analyses, tables, or figures may be omitted at interim analyses if there are insufficient data to warrant analysis or at the request of the SMC.

Analyses for the Primary Analysis Report will be finalized once the last participant has completed the Week 72 study visit on Step 1, all queries have been resolved, and the standard study database procedures have been completed.

Outlines of analyses for other objectives, including Step 2 follow up, and outcome measures not included in the Primary SAP will be provided in a separate SAP.

1.2 Version History

Version 2.0 of the A5354 SAP was created primarily in order to reflect changes made to the study in protocol v2.0.

One major change to the study in protocol v2.0 was an addition of 144 weeks of additional follow-up, incorporated as Step 2 of the study. Analyses for Step 2 will be encapsulated in a separate analysis plan.

Protocol v2.0 also states that the cell-associated DNA testing performed for the primary outcome measure at week 48 on Step 1 will be done separately by gag- and integrase-assays. Therefore, the analyses outlined for the primary outcome measure have been updated to reflect the pair of results that will be generated.

Version 3.0 of the A5354 SAP was updated to reflect changes to the study via LOA #1 and #2 to protocol version 2.0. Several secondary objectives and corresponding outcome measures were redesignated as exploratory objectives and 'other' outcome measures.

2 Study Overview

2.1 Study Design

A5354 is a phase II, prospective, open-label 2-step study to measure the effects of early antiretroviral therapy (ART) on the establishment of HIV-1 reservoir and HIV-1-specific immunity. Treatment-naïve participants with acute HIV-1 infection (AHI) will have an enrollment visit that will include the immediate initiation of ART. The primary outcome measure is cell-associated HIV-1 DNA (CAHD) in 5 million blood-derived CD4+ T-cells assayed by quantitative PCR (qPCR) at week 48 on Step 1.

A subset of participants who have completed week 48 on Step 1 will be consented for leukapheresis or large volume blood collection, cerebrospinal fluid collection via lumbar puncture, and gut biopsy via flexible sigmoidoscopy. Approximately 25 participants are estimated to have each optional procedure. Participants may consent to one or more of these optional procedures, which will be performed at any time on Step 1 from week 60 to week 72 in willing participants.

Willing participants who have completed Step 1 follow-up without meeting any criteria for permanent study discontinuation (per section 9.2) will be encouraged to continue on Step 2 and complete study evaluations through 144 weeks of Step 2 follow-up. Participants who had previously completed the study at week 72 per protocol version 1.0 will be allowed to re-enroll in protocol version 2.0 if they meet Step 2 eligibility criteria. The “re-enrolled” participants will be placed in their original Fiebig group that they were initially enrolled under protocol version 1.0

The Fiebig stage-classification system will be used to characterize the progression from HIV-1 exposure to HIV-1 seroconversion at the time of ART initiation. Plasma and serum samples will be collected at the time of ART initiation and the results of the Fiebig stage at ART initiation will be available to sites within 12 weeks. In this study, the Fiebig I-V stages of interest will be simplified into three study groups (based on HIV-1 antibody diagnostic profile at the time of ART initiation) as described below.

Group 1: Fiebig I/II (non-reactive HIV-1 antibody)

Group 2: Fiebig III/IV (reactive HIV-1 antibody and negative or indeterminate results on the Western blot or Geenius HIV-1/HIV-2)

Group 3: Fiebig V (reactive HIV-1 antibody and positive Western blot or Geenius HIV-1/HIV-2 without p31 band)

It is possible that a small number of participants will be determined to be in Fiebig VI (positive Western blot or Geenius HIV-1/HIV-2 with p31 band) based on analysis of the entry samples even though these participants are not specifically targeted for enrollment in this study. Participants who are determined to be in Fiebig VI will be followed on the study for no more than 24 weeks on Step 1, allowing ample time for them to pursue alternative sources for ART. Confirmed Fiebig VI participants will be replaced.

The Clinical Management Committee of the A5354 protocol team will review the Fiebig staging and ensure that these results are communicated to the site, as described in the study's Manual of Procedures.

2.2 Duration

Up to 216 weeks (72 weeks on Step 1 and 144 weeks on Step 2).

2.3 Sample Size

A total of 196 participants. Each study group had a target enrollment of 50 participants under protocol version 1.0. From these study groups, up to 25 eligible participants will be asked to consent to each optional procedure.

2.4 Population

Men and women 18 years and older with AHI. Pregnant and breastfeeding women are permitted to enroll in the study.

2.5 Regimen

The antiretroviral (ARV) regimen provided through the study is the single tablet regimen elvitegravir/cobicistat/emtricitabine/tenofovir alafenamide (EVG/COBI/FTC/TAF) or bictegravir/emtricitabine/tenofovir alafenamide (BIC/FTC/TAF). Other non-study-provided ARV regimens will be allowed for participants who are pregnant, breastfeeding, or unable/unwilling to take EVG/COBI/FTC/TAF or BIC/FTC/TAF, or for participants whose local health care/primary care provider prefers starting a different initial ARV regimen.

2.6 Hypotheses

Timing of antiretroviral therapy (ART) during different stages of acute HIV-1 infection (AHI) will be predictive of the magnitude and characteristics of HIV-1 reservoirs, and the quantity and quality of HIV-1-specific immune responses at week 48 on Step 1.

- ART initiation prior to HIV-1 antibody detection will be associated with limited or no detectable proviral DNA or HIV-1-specific immune responses at week 48 on Step 1.
- ART initiation in later AHI stages will be associated with larger HIV-1 reservoir establishment and quantitatively and qualitatively different HIV-1-specific immune responses at week 48 on Step 1.

2.7 Study Objectives

2.7.1 Primary Objectives

To compare the amount of cell-associated HIV-1 DNA (CAHD) in 5 million blood-derived CD4+ T-cells (assayed by quantitative PCR [qPCR]) at week 48 on Step 1 among participants who initiated ART in Fiebig I/II versus Fiebig III/IV versus Fiebig V and had sustained suppression of plasma HIV-1 RNA

2.7.2 Secondary Objectives

1. To evaluate HIV-1-specific CD4+ and CD8+ T-cells by flow cytometry while HIV-1 RNA is

suppressed on ART:

- a. magnitude and distribution of CD4+ and CD8+ T-cells responses to nef, gag, pol and env
 - b. quality of T-cell responses (i.e. frequency and type of polyfunctional responses)
2. To assess cell-associated HIV-1 DNA in participants prior to ART initiation.
 3. To establish a group of well-characterized, adults living with HIV who initiated ART during AHI that can serve as a source population for future ACTG studies, including those designed to test novel interventions to achieve HIV remission.

2.8 Overview of Sample Size Considerations

See protocol section 10.4 for details on the sample size considerations.

2.9 Overview of Formal Interim Monitoring

The study will be reviewed by a Study Monitoring Committee (SMC) according to ACTG standard operating procedures. The SMC will review accrual, baseline characteristics (including baseline laboratory values), Fiebig stage at ART initiation, AE summaries, CD4+ T-cell counts and HIV-1 RNA levels/suppression over time, study and ART discontinuations (and reasons), and completeness of follow-up and sample availability. The SMC will convene, at a minimum, 6 months after the first participant is enrolled or after 25 participants are enrolled, whichever is earlier and approximately annually thereafter or at the request of the SMC.

3 ANALYSIS REPORTS

3.1 Interim Analysis Reports

As outlined in the A5354 Study Progress, Data, and Safety Monitoring Plan (SPDSMP), an analysis report will be prepared and distributed for each SMC review. The report will be distributed to the SMC, DAIDS Clinical Representative, and the ACTG SDAC Coordinating Statistician for the SMC. The report will include analyses from the following sections of this analysis plan broken out by study group:

1. Accrual
2. Baseline characteristics
3. Fiebig stage summary (not included after accrual has completed)
4. Acute HIV-1 infection testing summary (not included after accrual has completed)
5. Study status and loss to follow-up
6. Antiretroviral treatment status
7. Adverse event summary
8. Pregnancy outcomes (if any)
9. CD4+ cell counts over time
10. Standard HIV-1 RNA copies/mL over time
11. Virologic failures
12. Summary of availability of results for primary outcome measure (not included after primary analysis is completed)
13. Summary of optional procedures performed and completed

3.2 Primary Analysis Report

Unless otherwise noted, the primary analysis report will include all sections in this analysis plan.

Section 5-8 have been summarized in a separate analysis report titled “Analysis report evaluating criteria for diagnosing acute HIV infection” (dated July 23, 2020). Unless there are additional data, analyses in these sections will not be included in the primary analysis report.

3.3 Lists of Data in Reports

Lists of data about individual study participants may be useful for interpreting the results of the study and so some lists are described below. To protect confidentiality, the content of these lists will be limited and for primary analyses will not include dates, participant identifier numbers or other combinations of information that might identify an individual participant.

4 GENERAL ANALYSIS CONSIDERATIONS

4.1 Definition of “study entry”, “baseline”, and “study group”

“Study entry” is defined as the study registration/randomization date. For the purposes of statistical analyses, study week 0 will include evaluations up to and including the date of study entry and, unless otherwise defined, baseline will be the last evaluation on or before the date of study entry.

The term ‘study group’ is used throughout this analysis plan to differentiate participants entering the study during Fiebig stages I-II (Group 1), stages III-IV (Group 2) and stage V (Group 3). At screening, a participant’s study group is estimated based on the available laboratory test results at the site. The estimated study group will be confirmed/rejected by centralized testing of samples taken at the entry visit. For interim analyses, participants who have yet to have the centralized Fiebig Stage result will be placed in a ‘Pending’ group. Once a participant’s centralized test result is available, they will then be grouped by these results. It is possible that a participant, who is estimated to be in one group at screening, will be found to be in a different group when the centralized results become available. At the primary analysis, it is intended that all participants will be grouped according to the results of the centralized testing.

Generally, tables will present results for the overall population and by study group. Select tables may also be presented by geographic region (domestic vs. international).

4.2 Period of Follow-up

Analyses in this document address the period of Step 1 follow-up defined by the protocol (up to 72 weeks following study entry). A separate analysis plan will describe the analyses for Step 2 follow-up (an additional 144 weeks following the completion of Step 1) as well as exploratory objectives.

4.3 Analysis Populations

All participants enrolled to the study will be included in accrual and centralized Fiebig result summaries.

Participants found to be HIV negative after enrollment will not be included in any summaries except those stated above. Participants found to be in Fiebig Stage VI will have baseline and select follow-up data summarized from the period of time prior to going off study (Week 24).

Analysis of the primary outcome measure will be restricted to study groups 1-3 (as determined by centralized testing), and only for participants who maintain HIV-1 RNA <50 copies/mL at week 48 with no ART interruption of ≥ 7 consecutive days and have available CAHD results from week 48 or week 49. Sensitivity analyses will include participants with extended periods of ART interruption (≥ 7 consecutive days) that maintained HIV-1 RNA <50 copies/mL at week 48.

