9.2 Premature Study Discontinuation

- Never started ART
- Started ART after 48 hours after enrollment and determined by the protocol team to be ineligible for continued participation
- Does not have HIV-1 infection
- **Participant confirmed to be Fiebig VI will discontinue after week 24 in Step 1.**
- Failure by the participant to attend three consecutive study visits
- Participant has **confirmed** VF as defined in [section 6.3.4](#)
- **In Step 1, interrupted ART ≥ 7 consecutive days and has not previously demonstrated an HIV-1 RNA < 50 copies/mL (prior to the interruption lasting ≥ 7 consecutive days)**
- Request by the participant to withdraw, **including withdrawal to enable participation in another study.**
- Request of the primary care provider if s/he thinks the study is no longer in the best interest of the participant.
- Participant judged by the investigator to be at significant risk of failing to comply with the provisions of the protocol as to cause harm to self or seriously interfere with the validity of the study results.
- At the discretion of the IRB/EC, NIAID, Office for Human Research Protections (OHRP), other government agencies as part of their duties, investigator, or industry supporter.

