7 FIEBIG STAGE

Tables showing the following:

- a. Cross tabulation of the study group estimated at entry, and that determined by centralized testing: number (%)
- b. Time (weeks) between study entry and Fiebig stage results (latest assay date) determined by centralized testing: N, mean, standard deviation, median and 25th and 75th percentiles
- c. Time (weeks) between screening and study entry: N, mean, standard deviation, median and 25th and 75th percentiles

- d. Fiebig stage determined by centralized testing: number (%) overall and by country
- e. Listing: Participants found to be HIV negative after enrollment, showing estimated Fiebig group at screening, screening assay timing/results, centralized assay timing/results, components and duration of ART regimen taken (if applicable), HIV-1 RNA assay results, site, and duration on study

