9.1 Study Status and Completeness of Follow-up of Participants

Table: Number (%) for the following categories:

- i. 'Completed Step 1 as defined by the protocol' or 'On study' (for interim analyses).
- ii. "Off study" due to death.
- iii. "Off study" prior to end of Step 1 follow-up (or, at interim analyses, prior to data retrieval date) for reasons other than death (with subcategories showing reason and whether or not prior to week 48 on Step 1).

Listing: Showing all premature discontinuations with centralized Fiebig Stage result, site, timing and reason of premature discontinuation, week of last clinic visit, ARV regimen taken, and whether a sample was collected at the week 48/49 visit.

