9.2 Duration of Follow-up Achieved

Table: Time (weeks) from study entry to last visit reported: median, 25th and 75th percentiles, minimum, and maximum.

NOTE: At the primary analysis, all analyses from here onwards will be undertaken after any exclusions from analyses. Participants who are determined to be Fiebig Stage VI by centralized testing will be followed and presented until they are taken off study at week 24.

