12 ADVERSE EVENTS

The protocol requires grading of events according to The Division of AIDS Table for Grading the Severity of Adult and Pediatric Adverse Events (DAIDS AE Grading Table), corrected Version 2.1, July 2017, which can be found on the DAIDS RSC website at <http://rsc.tech-res.com/clinical-research-sites/safety-reporting/daids-grading-tables>.

The protocol makes the following reporting requirements for signs and symptoms:

“At Step 1 entry, signs and symptoms of all grades that occurred within 30 days prior to entry must be recorded as medical history. Post-entry Grade ≥ 3 signs and symptoms and all signs and symptoms that led to a change in ART, regardless of grade”

The protocol makes the following reporting requirements for laboratory test abnormalities:

“At Step 1 entry, record all protocol-required laboratory values (performed by local laboratories) with exception of the urinalysis, regardless of grade. For post-entry assessments, record all laboratory values for creatinine, CrCl, AST (SGOT), and ALT (SGPT) regardless of grade. Post-entry Grade ≥ 2 laboratory findings and all laboratory findings that led to a change in ART, regardless of grade”

NOTE: Creatinine clearance should be graded using the categorical mL/min values from the DAIDS 2.1 toxicity grading tables, which begins with values below 90 mL/min. The percent change criteria will not apply to A5354. In Step 2, only creatinine clearance greater than Grade 2 should be reported.

The protocol makes the following reporting requirements for diagnoses:

“At Step 1 entry, all diagnoses that are described in protocol section 6.3.4 (Acute HIV-1, bone fractures, coronary heart disease, cancer, diabetes, tuberculosis, chronic hepatitis B or C, renal disease) must be recorded as medical history. Post-entry, record all targeted diagnoses (see list on the A5354 PSWP) and diagnoses that led to a change in ART.

NOTE: Uterine pregnancy does not require reporting as an AE (unless other SAE criteria are met) but must still be recorded in the eCRFs.”

Additionally, all AEs meeting the SAE definition or EAE reporting requirements, or led to a change in study treatment, must be reported.

For the purpose of ongoing safety monitoring occurring within A5354, the following data summaries will be provided at each interim analysis, separately for Step 1 and Step 2:

Table: summarizing number (%) of participants and the adverse events reported in the database, by MedDRA SOC, PT, grade and study group.

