Table: summarizing number (%) of participants and the serious adverse events reported in the database, by MedDRA SOC, PT, grade and study group.

Note: For participants enrolled to Step 2, AEs on Step 1 will be summarized up to last study visit on Step 1 in the primary analysis report of Step 1. Any AEs reported after the last visit on Step 1 prior to entry to Step 2 will be summarized in the analysis for Step 2 long-term follow-up.

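### Adverse events in uninfected participants who took ART would appear in no AE or SAE table of the primary analysis report

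*SAP*

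**What the plan says.** SAP 4.3 admits everyone enrolled to two kinds of summary, accrual and centralized Fiebig results, and then states: "Participants found to be HIV negative after enrollment will not be included in any summaries except those stated above". No safety summary is among the exceptions. SAP Section 5 names HIV-negative participants among the exclusions from analysis. The note in SAP 9.2 adds: "At the primary analysis, all analyses from here onwards will be undertaken after any exclusions from analyses".

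SAP Section 12 comes after that note. It plans a table "summarizing number (%) of participants and the adverse events reported in the database, by MedDRA SOC, PT, grade and study group" and a matching table for serious events. SAP 3.2 puts every section of the plan into the primary report unless otherwise noted, and nothing in Section 12 takes it out.

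On exposure, Protocol 2.1 (Urgency of ART Initiation) says that ART will not wait for HIV-1 test results in people likely to have acute infection. It foresees rare cases who prove uninfected, typically after three or fewer doses. Protocol 6.3.5 requires them to stop ART, attend a discontinuation visit and leave follow-up.

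**The concern.** Uninfected people who take ART bear drug risk without treatment benefit, and they are in that position because the design treats before confirmation. The protocol gives reasons why this brief exposure should be safe. Under the SAP as written, the primary report's AE tables cannot show whether it was. A reader who finds no row for these participants cannot tell whether no events occurred or whether events were not tabulated.

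The other replaced group is handled differently. Fiebig VI participants are also replaced, yet SAP 4.3 and the 9.2 note keep their data up to week 24. The SAP gives no reason for treating ART-exposed uninfected participants differently in safety reporting.

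**Working it through.** The point rests on the text; arithmetic is used only to gauge scale.

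**Do the rules reach the AE tables?**

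1. SAP 4.3: HIV-negative participants are in accrual and centralized Fiebig summaries only.
2. SAP 5: they are named as an analysis exclusion.
3. SAP 9.2 note: exclusions apply to all later sections at the primary analysis. Section 12 is later.
4. SAP 3.2: Section 12 belongs to the primary report.
5. SAP 4.1: study group means Groups 1-3, with a pending category at interim analyses only. An uninfected participant has no column in a table by study group.

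The Section 12 tables refer to events in the database, but that wording does not override the population rule in 4.3.

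**Does another planned output fill the gap?**

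| Output | What it may show | AE fields stated | In the primary report |
|---|---|---|---|
| SAP 5 list of exclusions | who was excluded and details | none | only if there are new data (SAP 3.2) |
| SAP 7, listing (e) | "components and duration of ART regimen taken (if applicable), HIV-1 RNA assay results, site, and duration on study" | none | only if there are new data (SAP 3.2) |
| SAP 9.1 listing | "all premature discontinuations with centralized Fiebig Stage result, site, timing and reason of premature discontinuation, week of last clinic visit, ARV regimen taken" | none | yes, if 4.3 does not bar them |

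The 9.1 listing could reach these people because Protocol 9.2 includes "Does not have HIV-1 infection" as a reason for discontinuation. On Sections 5-8, SAP 3.2 says that they "have been summarized in a separate analysis report titled" and dates that report July 2020. Its content is not available here.

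**How many people?**

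Inputs: planned total 196 and 36 further enrolments after replacing Fiebig VI and HIV-negative participants (Protocol 10.4); 168 enrolled by 22 May 2019 (Protocol 2.1, Feasibility); Groups 1, 2 and 3 at 37, 63 and 54, in the paragraph of 10.4 that cites staging data of 15 May 2019.

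- Counted toward the total: 196 − 36 = 160.
- Enrolled but not counted: 168 − 160 = 8, and 8/168 = 4.8%. This is Fiebig VI and HIV negative combined.
- Outer bound: 37 + 63 + 54 = 154; 168 − 154 = 14, and 14/168 = 8.3%. The further 160 − 154 = 6 were probably not yet staged.

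The HIV-negative number at that date therefore lies between 0 and about 8, with 14 as an outer bound. It is approximate because the two dates differ by a week, and later enrolments are not covered.

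**The case against.** The strongest reply is that the exclusion is deliberate and harmless. SAP 4.3, 5 and 9.2 agree with one another. Safety is not a stated objective or outcome measure. Section 12 introduces its tables for ongoing monitoring at interim analyses. The protocol calls such cases rare, cites a positive predictive value of nearly 100% for the entry criteria based on the signal-to-cutoff ratio, and expects very brief exposure. A handful of people would yield little interpretable AE information. All of this limits the importance of the point. It does not put the events into the report, and SAP 3.2 still brings Section 12 into it.

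Four stronger readings are tempting, and the documents do not support them.

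- *Safety oversight fails.* It does not. Protocol 7.2 requires AEs meeting its criteria to be recorded, 7.3.2 sets expedited reporting of serious events, 6.3.5 provides a discontinuation visit, and 10.5 has the team monitor all reported AEs and lets it ask the Study Monitoring Committee to review all safety data.
- *About eight uninfected people were treated.* The 8 includes Fiebig VI and is not split. Those participants enrolled before Version 2.0 (dated 12/31/19), so the current entry routes that need no prior RNA result cannot explain the count.
- *These events are reported nowhere.* The July 2020 report is not available, so only the primary report can be judged. Interim tables are unclear: 4.3 has no time limit, while the 9.2 note speaks of the primary analysis.
- *The SAP expressly promises these participants' AEs in the primary report.* Section 12 does say "AEs on Step 1 will be summarized up to last study visit on Step 1 in the primary analysis report of Step 1", but that sentence concerns people who enter Step 2. Uninfected participants leave follow-up and cannot be among them, so it supports neither side.

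**Conclusion.** The point holds as a gap in the completeness of safety reporting. A stated population rule, rather than a missing detail, removes ART-exposed uninfected participants from the AE and SAE tables of the primary report, and no other output planned for that report has AE fields for them.

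The consequence is small. The number affected is unknown and may be zero. The figure of about 8 of 168 is a combined count and assumes that the 36 further enrolments were reckoned net of all replacements. No efficacy conclusion changes, and excluding these participants from the CAHD analysis is correct. The change is worth making because it is cheap and lets the report state a result, even if that result is none.

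**What to change.** Add to SAP 4.3: *The HIV-negative exclusion does not apply to safety reporting for anyone who took at least one dose of ART on study.* This sentence also settles how interim AE tables treat these participants.

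In Section 12 of the primary report, give the number of ART-exposed HIV-negative participants and their AEs and SAEs by term and grade, in a separate row or column. Keep them out of Groups 1-3 and out of the existing overall column, so that those denominators do not change. With one or two people, an aggregate row is close to individual data, so apply the confidentiality limits of SAP 3.3 to any row, column or listing. If there are no such participants or no events, state that.

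The cost is one sentence and slight extra programming. The AE data are already on the eCRF, and the primary analysis is untouched.
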